| elido_controlled | 0.1, CURRENT; Most-Recent; In Review | 090032d580f4eeeb | |
| Reason For Issue | | | |

Potassium Nitrate / Sodium Fluoride

208078

Final Statistical Reporting and Analysis plan Addendum 1, 01FEB2018

| SAP Analysis Plan Amendment 1 | Statistical Analysis Plan Addendum | Rationale for Changes |
|-------------------------------|------------------------------------|--|
| | | 
means and CI will be more appropriate. This adjusted means will be used for ranking the study treatments for interpretation. Therefore it was decided to include the figures based on adjusted means change from baseline (+/- 95% CIs) in the RAP addendum.
 
 While creation of the Figure 14.2.2 as part of non-topline delivery, it was observed that the presentation of Figure 14.2.2 in RAP amendment template was not appropriate. Therefore it was decided to change the presentation of Figure 14.2.2 to be consistent with Figure 14.2.4. |

| | | | | |
|---|----------------------|--|----------------------------|-----------------------|
|  GlaxoSmithKline | Document Name | gsk-208078-reporting-and-analysis-plan.pdf | | |
| Type | Version | 0.1; CURRENT; Most-Recent; In Review | Document Identifier | Effective Date |
| elido controlled | | 090032d580f4eeeb | | |
| Reason For Issue | | | | |

Potassium Nitrate / Sodium Fluoride

208078

Final Statistical Reporting and Analysis plan Addendum 1, 01FEB2018

7 Attachment 1: List of Data Displays

Study 208078_List of
Outputs.xlsx

| | | | |
|------------------|--|---------------------|----------------|
| Document Name | gsk-208078-reporting-and-analysis-plan.pdf | | |
| Type | Version | Document Identifier | Effective Date |
| elido controlled | 0.1; CURRENT; Most-Recent; In Review | 090032d580f4eeeb | |
| Reason For Issue | | | |

Potassium Nitrate / Sodium Fluoride

208078

Final Statistical Reporting and Analysis plan Addendum 1, 01FEB2018

8 Appendix 1: Template for Tables, Figures and Listings

[figure not shown]
Protocol 208078

Program Run Date: DDMMYYYY

Figure 14.2.3

Change from Baseline in Overall MLSI (AxI) Score Adjusted Means (\pm 95%CIs) Plot Over Time by Treatment Intent-to-Treat Population

Study Population: Intent-to-Treat Population (N=XX)

Values are adjusted means \pm 95%CIs

PPD

Test Product 1: 5% KNO₃ / 0.2542% NaF dentifrice with 0.5% spherical silica (RDA~38)

Test Product 2: 5% KNO₃ / 0.2542% NaF dentifrice with 1% spherical silica and 5% STP (RDA~58)

Reference Product 1: Sensodyne Pronamel Daily Protection (RDA~36).

| | | | |
|------------------|--|---------------------|----------------|
| Document Name | gsk-208078-reporting-and-analysis-plan.pdf | | |
| Type | Version | Document Identifier | Effective Date |
| elido controlled | 0.1; CURRENT; Most-Recent; In Review | 090032d580f4eeeb | |
| Reason For Issue | | | |

Potassium Nitrate / Sodium Fluoride

208078

Final Statistical Reporting and Analysis plan Addendum 1, 01FEB2018

Reference Product 2: Sensodyne Extra Whitening (RDA~166).

PPD

Programming Note: 1) Adjusted Means and CIs plotted are from summary statistics PPD .
2) Baseline should start from zero and CIs should not applicable.

| | | | |
|------------------|--|---------------------|----------------|
| Document Name | gsk-208078-reporting-and-analysis-plan.pdf | | |
| Type | Version | Document Identifier | Effective Date |
| eldo controlled | 0.1; CURRENT; Most-Recent; In Review | 090032d580f4eeeb | |
| Reason For Issue | | | |

Potassium Nitrate / Sodium Fluoride

208078

[figure not shown]
Final Statistical Reporting and Analysis plan Addendum 1, 01FEB2018

Protocol 208078

Program Run Date: DDMMYYYY

Figure 14.2.4
Change from Baseline (Pre-brushing) in Overall TPI Score Adjusted Means ($\pm 95\% \text{CI}$) Plot Over Time by Treatment Intent-to-Treat Population

Study Population: Intent-to-Treat Population (N=XX)

Test Product 1: 5% KNO₃ / 0.2542% NaF dentifrice with 0.5% spherical silica (RDA~38)

Test Product 2: 5% KNO₃ / 0.2542% NaF dentifrice with 1% spherical silica and 5% STP (RDA~58)

Reference Product 1: Sensodyne Pronamel Daily Protection (RDA~36).

| | | | |
|------------------|--|---------------------|----------------|
| Document Name | gsk-208078-reporting-and-analysis-plan.pdf | | |
| Type | Version | Document Identifier | Effective Date |
| eldo controlled | 0.1; CURRENT; Most-Recent; In Review | 090032d580f4eeeb | |
| Reason For Issue | | | |

Potassium Nitrate / Sodium Fluoride

208078

Final Statistical Reporting and Analysis plan Addendum 1, 01FEB2018

Reference Product 2: Sensodyne Extra Whitening (RDA~166).

Programming Note: 1) Adjusted Means and CIs plotted are from summary statistics **PPD**
2) Baseline should start from zero and CIs should not applicable.

PPD

Note: Use the same template as Figure 14.2.4 for the figure 14.2.2.

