4.1 Inclusion Criteria

Subject eligibility should be reviewed and documented by an appropriate member of the investigator's study team before subjects are included in the study.

Subjects must meet all of the following inclusion criteria to be eligible for enrollment into the study:

1. Evidence of a personally signed and dated informed consent document indicating that the subject has been informed of all pertinent aspects of the study before any assessment is performed.
2. Male and female subjects who, at the time of screening, are between the ages of 18 and 65 years, inclusive.
3. Subjects who are willing and able to comply with scheduled visits, treatment plan, and other study procedures.
4. Good general and mental health with, in the opinion of the investigator or medically qualified designee no clinically significant and relevant abnormalities of medical history or oral examination which could impact study outcomes.
5. Good general and mental health with, in the opinion of the investigator or medically qualified designee an absence of any condition that would impact on subject safety or wellbeing, or affect the subject's ability to understand and follow study procedures and requirements.
6. In the opinion of the investigator or medically qualified designee, **at screening**, subjects must have good oral health.
7. In the opinion of the investigator or medically qualified designee, **at screening**, subjects must have at least 20 natural teeth including the 12 anterior teeth, gradable for TPI (Gradable teeth are those where restorative materials cover less than 25% of the tooth surface to be graded).
8. In the opinion of the investigator or medically qualified designee, **at screening**, subjects must have the facial surfaces of at least 4 of the anterior teeth, gradable for the MLSI.
9. In the opinion of the investigator or medically qualified designee, **at screening**, subjects must have the presence of extrinsic dental stain (judged to be formed due to dietary

GlaxoSmithKline Consumer Healthcare Confidential

Template Version Effective: 22-Jun-2017

Page 21 of 61

Document Name	093270B076tpcoctol.pdf	Document Identifier	Effective Date
Type	Version		
eldo_clinicalelbc	0.0. DIFFERENT MESSER Revision CURRENT	1090032d580f8944c	14-Aug-2017 09:06:22

Potassium Nitrate / Sodium Fluoride

208078

Final 1.0 Clinical Protocol

factors) on the facial surfaces of the anterior teeth, as determined from a visual MLSI stain assessment.

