7.1.1 Macpherson Modification of the Lobene Stain Index (MLSI)

Stain assessments will be performed by a single clinical examiner, in the same room with consistent light levels, throughout the study to facilitate standardization of the assessments. Subjects will brush their anterior teeth with a wetted toothbrush for 30 seconds prior to each stain assessment. Teeth will be air dried prior to the assessment, and during the assessment as needed.

GlaxoSmithKline Consumer Healthcare Confidential

Template Version Effective: 22-Jun-2017

Page 37 of 61

Document Name	098270B076ClinicalProtocol.pdf	Document Identifier	Effective Date
Type	Version		
eldo_clinicalProtocol	0.0. DIFFERENT MSLI Version CURRENT	1090032d580f8904c	14-Aug-2017 09:06:22

Potassium Nitrate / Sodium Fluoride

208078

Final 1.0 Clinical Protocol

The facial surfaces of each assessable tooth is divided into four regions. The ‘gingival’ region is defined as a crescent-shaped band, approximately 2 mm wide, adjacent to the free margin of the gingiva and extending to the crest of the interdental papillae of the adjacent teeth. The ‘body’ of the tooth is then sub-divided into three regions on the facial surfaces.

- **Maxillary and mandibular facial surfaces:** distal facial area; body facial area; mesial facial area

Extrinsic dental stain will be scored in each area using the MSLI [MacPherson, 2000], with grades of 0-3 assigned for each category of intensity and area.

Stain Intensity: intensity will be scored separately for the ‘gingival’ and ‘body’ areas of each assessable tooth as follows.

- Score 0 = No stain
- Score 1 = Light stain
- Score 2 = Moderate stain
- Score 3 = Heavy stain

Stain Area: area will be scored separately for the ‘gingival’ and ‘body’ areas of each assessable tooth as follows.

- Score 0 = No stain
- Score 1 = Stain covering up to 1/3 of region
- Score 2 = Stain covering up to 1/3 of region, and no more than 2/3 of region
- Score 3 = Stain covering more than 2/3 of region

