7.1.1.1 Repeatability of the MSLI Assessment

To assess the repeatability of the stain assessments, replicate examinations will be performed by the same qualified dental examiner at each assessment visit. Five subjects will be randomly selected for repeat MSLI assessments across each assessment window (a total of 20 repeat MSLI assessments over the duration of the study). Every effort should be made to ensure the examiner does not refer to the results of the assessment completed prior to the repeat assessment. The results of the initial assessment will not be visible to the examiner or scribe when the repeat assessment is carried out.

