7.1.2 Turesky Modification of the Quigley Hein Index Dental Plaque Assessment (TPI)

The qualified dental examiner must ensure that the subjects taking part in this exercise have been appropriately informed and have consented to take part to this activity.

GlaxoSmithKline Consumer Healthcare Confidential

Template Version Effective: 22-Jun-2017

Page 38 of 61

Document Name	003208076tprotocol.pdf	Document Identifier	Effective Date
Type	Version		
eldo_clinicalellbc	0.0. DIFFERENT MESSER Revision CURRENT	1090032d580f894bc	14-Aug-2017 09:06:22

Potassium Nitrate / Sodium Fluoride

208078

Final 1.0 Clinical Protocol

The dental examiner will use the Turesky Modification of the Quigley Hein Index [Turesky 1970], to assess plaque on all gradable teeth for the full mouth. Only natural teeth devoid of restorations which would prevent plaque grading can be assessed. This means no crowns, bridges, and teeth with restorations which, in the investigator's judgment would prevent an accurate grading. Wisdom teeth are not to be assessed.

The plaque will first be disclosed using a dye solution (provided by site). Subjects will then rinse with 5 millilitres (mL) of Trace Disclosing Agent for 10 seconds to disclose any residual plaque. They will expectorate and rinse with 10 mL of water for 10 seconds and expectorate again. Plaque will be assessed with each tooth being divided into 6 areas including the mesiofacial, facial, distofacial, mesiolingual, lingual and distolingual surfaces.

Disclosed plaque will be scored as follows and recorded in the CRF:

Score	Description
0	No plaque
1	Slight flecks of plaque at the cervical margin of the tooth
2	A thin continuous band of plaque (1 mm or smaller) at the cervical margin of the tooth
3	A band of plaque wider than 1 mm but covering less than 1/3 of the crown of the tooth
4	Plaque covering at least 1/3 but less than 2/3 of the crown of the tooth
5	Plaque covering 2/3 or more of the crown of the tooth

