7.1.2.1 Repeatability of the Plaque Assessment

To assess the repeatability of the TPI assessments, replicate examinations will be performed by the same qualified dental examiner at each assessment visit. Five subjects will be randomly selected for repeat TPI examinations across each assessment window (a total of 10 repeat TPI examinations over the duration of the study). Repeatability assessments will be a minimum of 10 minutes between repeat plaque assessments of the same subject. The results of the initial assessment will not be visible to the examiner or scribe when the repeat assessment is carried out.

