10.2.5.3 Analysis of exploratory variables

The change from baseline in TPI variables will be analysed using analysis of covariance (ANCOVA) with treatment and MLSI stratification as fixed effects and appropriate baseline (pre-treatment) TPI as a covariate.

The repeat stain and plaque assessments will be compared to the original assessments and will not be used in any efficacy analysis. The first and second assessments on each tooth site will be cross tabulated. A weighted Kappa coefficient (κ), along with the 95% CI will be calculated to assess the intra-examiner reliability. Fleiss-Cohen weighted kappa will be calculated for the repeatability analysis. Reliability will be deemed

- Excellent if $\kappa > 0.75$
- Fair to good if $0.4 \leq \kappa \leq 0.75$
- Poor if $\kappa < 0.4$

All subjects who have repeatability data will be included in this analysis.

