4.8 Analysis of Other Variables

To assess the repeatability of the stain and TPI assessments, replicate examinations will be performed by the same qualified dental examiner at each assessment visit. Five subjects will be randomly selected for repeat MLSI and TPI assessments across each assessment window.

The repeat stain and plaque assessments will be compared to the original assessments and will not be used in any efficacy analysis. The first and second assessments on each tooth site will be cross tabulated. A weighted Kappa coefficient (κ), along with the 95% CI will be calculated to assess the intra-examiner reliability. Fleiss-Cohen weighted kappa will be calculated for the repeatability analysis. Reliability will be deemed

- Excellent if $\kappa > 0.75$
- Fair to good if $0.4 \leq \kappa \leq 0.75$
- Poor if $\kappa < 0.4$

All subjects who have repeatability data will be included in this analysis. Results for repeat MLSI area and intensity assessments will be in [Table 14.2.8.1](#) and [Table 14.2.8.2](#) respectively. Also result for repeat TPI assessment will be [Table 14.2.8.3](#).

5 Changes to the Protocol Defined Statistical Analysis Plan

Changes from the originally planned statistical analysis specified in the protocol are outlined in Table 1.

Table 1 Changes to Protocol Defined Analysis Plan

| Protocol | Reporting & Analysis Plan | |
|------------------------------|---------------------------|-----------------------|
| Statistical Analysis section | Statistical Analysis Plan | Rationale for Changes |

GlaxoSmithKline Consumer Healthcare Confidential

Page 17 of 53

| | | | |
|------------------|--|---------------------|----------------|
| Document Name | gsk-208078-reporting-and-analysis-plan.pdf | | |
| Type | Version | Document Identifier | Effective Date |
| elido_controlled | 0.1, CURRENT; Most-Recent; In Review | 090032d580f4eeeb | |
| Reason For Issue | | | |

Potassium Nitrate / Sodium Fluoride

208078

Final Statistical Reporting and Analysis plan Amendment 21NOV2017

| Protocol | Reporting & Analysis Plan | |
|---|--|---|
| Statistical Analysis section | Statistical Analysis Plan | Rationale for Changes |

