[1] From ANCOVA with treatment and MLSI stratification as factors and appropriate baseline (Pre-treatment) TPI score as a covariate

[2] Difference is first named treatment minus second named treatment such that a negative difference favours the first named treatment

Page x of y

PPD

Programming note: The same summary would be provided for the Week 8 pre-brushing and Week 8 post-brushing also.

GlaxoSmithKline Consumer Healthcare Confidential

Page 34 of 53

| | | | | |
|------------------|--|------------------|---------------------|----------------|
| Document Name | gsk-208078-reporting-and-analysis-plan.pdf | | | |
| Type | Version | | Document Identifier | Effective Date |
| elido controlled | 0.1; CURRENT; Most-Recent; In Review | 090032d580f4eeeb | | |
| Reason For Issue | | | | |

Potassium Nitrate / Sodium Fluoride

208078

Final Statistical Reporting and Analysis plan Amendment 21NOV2017

Protocol 208078

Program Run Date: DDMMYYYY

Table 14.2.8.1
Repeatability for MLSI Intensity Score
MLSI Repeatability Population

Study Population: MLSI Repeatability Population (n=XX)

| Initial \ Repeated | Missing | 0 | 1 | 2 | 3 |
|--------------------|--------------|----|----|----|----|
| Missing | xx | xx | xx | xx | xx |
| 0 | xx | xx | xx | xx | xx |
| 1 | xx | xx | xx | xx | xx |
| 2 | xx | xx | xx | xx | xx |
| 3 | xx | xx | xx | xx | xx |
| Kappa | 0.xx | | | | |
| 95% CI | (0.xx, 0.xx) | | | | |

Intensity Score: 0=No Stain; 1=light Stain; 2=Moderate Stain; 3=Heavy Stain. Missing means non-scorable.

Page x of y

PPD

██████████

Note to Programmer: For Table 14.2.8.2 and 14.2.8.3, use area and TPI scoring descriptions in footnote.

| | | | |
|------------------|--|---------------------|----------------|
| Document Name | gsk-208078-reporting-and-analysis-plan.pdf | | |
| Type | Version | Document Identifier | Effective Date |
| elido controlled | 0.1; CURRENT; Most-Recent; In Review | 090032d580f4eeeb | |
| Reason For Issue | | | |

Potassium Nitrate / Sodium Fluoride

208078

Final Statistical Reporting and Analysis plan Amendment 21NOV2017

Protocol 208078

Program Run Date: DDMMYYYY

Table 14.3.1.1.1
Treatment Emergent Adverse Event by SOC and Preferred Term
Safety Population

| Study Population: Safety Population (N=xx) | | Test Product 1 (N=XX) | | Test Product 2 (N=XX) | | Reference Product 1 (N=XX) | | Reference Product 1 (N=XX) | | Overall (N=XX) | |

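### The 95% CI for the repeatability kappa ignores that tooth sites are clustered within subjects, so it would be too narrow, materially for TPI and mildly for MLSI

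*SAP*

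**What the plan says.** Protocol 10.2.5.3 and SAP 4.8 describe the same repeatability analysis. The unit is the tooth site: "The first and second assessments on each tooth site will be cross tabulated". A Fleiss-Cohen weighted kappa is then computed, "along with the 95% CI will be calculated to assess the intra-examiner reliability". The Table 14.2.8.1 template in SAP Appendix 1 is one pooled table with one kappa and one 95% CI. Neither document names a variance estimator, a subject-level bootstrap or any other allowance for sites within a subject.

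The sampled unit is the subject: five are drawn at random in each assessment window. Protocol 7.1.1.1 gives "a total of 20 repeat MSLI assessments over the duration of the study" and Protocol 7.1.2.1 gives "a total of 10 repeat TPI examinations over the duration of the study". Reliability is graded by cut-offs of 0.4 and 0.75 on kappa itself, and the repeat data enter no efficacy analysis.

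**The concern.** The usual standard error of kappa from a cross-tabulation assumes independent pairs. Sites in one mouth share that subject's stain or plaque level, and sites scored in one sitting may also share a small shift in the examiner's threshold. Adding sites within a mouth therefore adds less information than adding subjects, and a site-level interval overstates precision.

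TPI is more exposed because it has the most sites per examination and the fewest examinations. A single examiner scores every subject (Protocol 1.2.2), so this kappa is the planned quantitative evidence that scoring is consistent. The interval tells the reader how secure a label such as excellent is after 10 repeat plaque examinations.

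**Working it through.** **Reproducing the plan's counts.** MLSI is repeated in four windows (baseline and Weeks 2, 4 and 8): 5 × 4 = 20. TPI is repeated in two (baseline and Week 8): 5 × 2 = 10. Both match the protocol.

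**Site pairs.**
- MLSI: 4 assessment teeth (Protocol 6.1.2). "The facial surfaces of each assessable tooth is divided into four regions" (Protocol 7.1.1). 4 × 4 = 16 sites per examination, and 20 × 16 = 320 pairs.
- TPI: "subjects must have at least 20 natural teeth including the 12 anterior teeth, gradable for TPI" (Protocol 4.1), and wisdom teeth are not scored, so 20 to 28 teeth. "Plaque will be assessed with each tooth being divided into 6 areas" (Protocol 7.1.2). 20 × 6 = 120 to 28 × 6 = 168 sites per examination, and 10 × 120 = 1,200 to 10 × 168 = 1,680 pairs.

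**Design-effect check.** With m sites per examination and within-subject correlation ICC of the contributions to kappa, the interval should be wider by √(1 + (m − 1) × ICC). The ICC is not in the documents, so a range is shown.

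| Assumed ICC | MLSI, m = 16 | TPI, m = 120 | TPI, m = 168 |
|---|---|---|---|
| 0.01 | 1.07 | 1.48 | 1.63 |
| 0.02 | 1.14 | 1.84 | 2.08 |
| 0.05 | 1.32 | 2.64 | 3.06 |
| 0.10 | 1.58 | 3.59 | 4.21 |

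For example, TPI with m = 120 and ICC 0.05: √(1 + 119 × 0.05) = √6.95 = 2.64, so 1,200 pairs are worth 1,200 / 6.95 ≈ 173. For MLSI at the same ICC, 320 / 1.75 ≈ 183.

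**Simulation.** Clustered ordinal scores were generated in pairs, with 2,000 data sets per setting. Assumptions: 10%, 25% or 40% of latent score variance between subjects; an examination-level shift with SD 0, 0.1 or 0.2; site error SD 0.4. True kappa was 0.76-0.82. The empirical SD of the quadratic-weighted kappa was compared with its standard large-sample SE.

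| | MLSI (20 × 16) | TPI (10 × 120-168) |
|---|---|---|
| No clustering: SD/SE, coverage | 1.01, 94% | 0.98, 96% |
| Clustered: SD/SE | 0.99-1.34 | 1.16-3.53 |
| Coverage of standard 95% CI | 85-95% | 40-92% |
| Median half-width, standard | 0.042-0.048 | 0.016-0.022 |
| Median half-width, by subject | 0.045-0.068 | 0.022-0.072 |
| Coverage, subject jackknife with t limits | 95-96% | 89-96% |

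The standard interval is right when there is no clustering, so the loss comes from clustering.

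**Other models.** With tooth effects added and error SD allowed to differ between subjects, low to moderate clustering gave SD/SE of 0.99-1.29 for MLSI and 1.15-2.87 for TPI. Strong clustering gave 1.25-1.55 and 2.9-4.4. With equal-frequency score categories the ratios were 1.04-1.23 and 1.14-2.86.

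**What a reader would see.** Take a TPI kappa of 0.79 as an illustration. At ±0.022 the interval is 0.768-0.812, clear of the 0.75 cut-off. At ±0.072 it is 0.718-0.862, which includes it.

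**The case against.** - **Little depends on this interval.** The label uses the point estimate, no decision rule uses the CI, and the study is described as an exploratory proof of principle. This stands, and it limits the importance of the point.
- **The size is assumed.** A further TPI simulation (10 × 150) gave SD/SE of 1.20-1.44 at a 10% between-subject share, about 2.0 at 25%, and 2.9-3.0 only at 40%. Inclusion Criterion 11 (pre-brushing TPI of at least 2.0) removes subjects with low plaque, which argues against the top of that range. This also stands: the direction is firm, the size is not.
- **The target of inference matters.** If the selected subjects' true scores are held fixed and only examiner error varies, the standard SE is conservative for MLSI (SD/SE 0.78-0.86). For TPI it is also conservative at a shift SD of 0-0.1 (0.78-0.85), and only mildly short at 0.2 (1.11-1.25, coverage 90-92%). Most of the TPI inflation therefore comes from which subjects are drawn. Because subjects are selected at random so that the result speaks for the trial's scoring as a whole, generalising beyond them is the natural target. The SAP should still say so.
- **The MLSI effect is small and its site count is uncertain.** Protocol 7.1.1 defines four regions but can be read as scoring only gingival and body areas. That would give 8 sites and 160 pairs, for which SD/SE was 1.01-1.16 in one simulation and up to 1.30 under strong clustering in another. The MLSI effect is accordingly described only as mild.
- **The CI method is not named.** Use of the independence-based interval is inferred from the pooled table. That silence is the gap: a programmer following the SAP would have no reason to do anything else.

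**Conclusion.** The concern holds. As written, the plan leads to a site-level interval that is too narrow when read as a statement about subjects like those in the trial. Under the assumed clustering, the standard error is understated by a factor of about 1.2 to 3.5 for TPI; for MLSI the factor runs from about 1.0 (no understatement) to 1.3. The contrast between the indices follows from the protocol's own counts; the absolute size depends on a correlation that the documents do not give. If a subject is drawn in more than one window, which the plan does not exclude, there are fewer than 20 or 10 independent clusters and the shortfall grows. The consequence is confined to the reported precision of examiner reliability. It should be corrected because the correction is almost free.

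**What to change.** Keep kappa, its weights and the label cut-offs. Add to SAP 4.8:

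*The 95% CI for kappa will be obtained by a delete-one-subject jackknife with t limits on (number of subjects − 1) degrees of freedom. All sites and all repeat examinations of the same subject form one cluster. The interval refers to the population of subjects from which the repeat subjects were drawn.*

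In Tables 14.2.8.1 to 14.2.8.3, show the number of subjects beside the number of site pairs. The template header already carries a population count ("Study Population: MLSI Repeatability Population (n=XX"), so this is a small clarification.

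The cost is a few lines of code, a short addition to the SAP and one table row, with no new data. The interval will be wider and less favourable. With at most 10 TPI clusters it still falls slightly short in the most clustered settings (89-92% coverage), but that is far better than the roughly 40% of the standard interval at the strong end. Another subject-level method would also meet the need, provided the SAP names it.
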